#### 5.2.1.8. Overdose Precautions

In Phase 1 studies, an MTD for idelalisib was not reached when administering the drug continuously at dose levels of 350 mg BID (700 mg per day) {[Coutre 2011](#), [Kahl 2011](#)}. However, in this protocol, an overdose is defined as administration of more than the prescribed daily dose.

In a subject who experiences an overdose, consideration should be given as to whether idelalisib administration should be temporarily interrupted. If the overdose ingestion is recent and substantial, and if there are no medical contraindications, use of gastric lavage or induction of emesis may be considered. Observation for any symptomatic side effects should be instituted, and biochemical and hematological parameters should be followed closely (consistent with the protocol or more frequently, as needed). Appropriate supportive management to mitigate adverse effects should be initiated.

The Gilead Sciences medical monitor should be contacted if a study drug overdose occurs. Cases of study drug overdose will result in specific reporting requirements (see Section 8.6).

#### 5.2.1.9. Inadvertent Exposure and Spill Precautions

Based on available data from nonclinical studies, idelalisib does not appear to be acutely toxic, genotoxic, or irritative at levels that are likely to result from inadvertent exposure to the contents of broken tablets. However, personnel handling the drug should use reasonable precautions to avoid eye contact, skin contact, inhalation, or ingestion of the study drug product. For further information regarding inadvertent exposure and spill precautions, please consult the idelalisib investigator brochure.

### 5.2.2. Ofatumumab

#### 5.2.2.1. Description

Ofatumumab (Arzerra®) is a human monoclonal IgG1 kappa antibody directed against the CD20 antigen found on pre-B and mature B cells. Ofatumumab is generated with hybridoma technology by using HCo7 and KM transgenic mice and is produced in a recombinant murine cell line (NS0) {Teeling 2004}. The protein has an approximate molecular weight of 149 kD.

For pharmaceutical use, the drug is provided as a sterile, colorless, preservative-free liquid concentrate containing 20 mg/mL for dilution and intravenous administration. Inactive ingredients include: 10 mg/mL arginine, diluted hydrochloric acid, 0.019 mg/mL edetate disodium, 0.2 mg/mL polysorbate 80, 6.8 mg/mL sodium acetate, 2.98 mg/mL sodium chloride and Water for Injection, USP. The pH of the solution is 5.5.

#### 5.2.2.2. Packaging

Ofatumumab is supplied in single-use 100-mg/5-ml vials or 1,000-mg/50-mL vials.

#### 5.2.2.3. Source

Ofatumumab will be supplied free of charge by Gilead Sciences and commercial ofatumumab may be supplied through a vendor, as needed.

#### 5.2.2.4. Storage and Stability

Ofatumumab vials are stable at 2 °C–8 °C (36 °F–46 °F). Vials should be protected from light and should not be frozen or shaken.

Diluted ofatumumab solutions for infusion may be stored at 2 °C–8 °C (36 °F–46 °F). The infusion should be started within 12 hours of ofatumumab preparation. Prepared solution should be discarded after 24 hours from constitution.

#### 5.2.2.5. Solution Preparation and Dispensing

The clinic staff (eg, pharmacist or other qualified person) will be responsible for preparing ofatumumab. A qualified person (eg, nurse or physician with experience in monitoring the administration of chemotherapeutic agents) will be responsible for infusing ofatumumab.

Before use, the ofatumumab vials should be visually inspected for particulate matter and discoloration. The solution should be colorless and may contain a small amount of visible translucent-to-white, amorphous, ofatumumab particles. The solution should not be used if discolored or cloudy, or if foreign particulate matter is present.

For the preparation of each 300-mg dose of ofatumumab, 15 ml should be withdrawn from a 1,000-mL polyolefin or PVC bag of 0.9% Sodium Chloride Injection, USP and discarded, and 5 mL from each of 3 vials containing 100 mg/5 mL of ofatumumab should be aseptically added to the bag.

For the preparation of each 1,000-mg dose of ofatumumab, 50 ml should be withdrawn from a 1,000-mL polyolefin or PVC bag of 0.9% Sodium Chloride Injection, USP and discarded, and 50 mL from a vial containing 1000 mg/50mL of ofatumumab should be aseptically added to the bag.

For the preparation of each 2,000-mg dose of ofatumumab, 100 ml should be withdrawn from a 1,000-mL polyolefin or PVC bag of 0.9% Sodium Chloride Injection, USP and discarded, and 50 mL from each of 2 vials containing 1000 mg/50 mL of ofatumumab should be aseptically added to the bag.

The diluted solution should be mixed by gentle inversion. The infusion solution should not be mixed or diluted with other drugs.

Using an infusion pump, ofatumumab should be administered via polyvinyl chloride administration sets and through an in-line filter. The intravenous line should be flushed with 0.9% Sodium Chloride Injection, USP before and after each dose.

#### 5.2.2.6. Accountability

The disposition of all ofatumumab should be documented from the time of receipt at the site through subject dispensing and return.

Study personnel must ensure that all study drug is kept in a secure locked area with access limited to authorized personnel. The study drug must not be used outside the context of this protocol. Under no circumstances should the investigator or site personnel supply study drug to other investigators or clinics, or allow the study drug to be used other than as directed by this protocol.

The investigator and/or the responsible site personnel must maintain accurate records of the receipt of all study drug shipped by Gilead Sciences or its designee, including, but not limited to, the date received, lot number, amount received, and the disposition of all study drug. Upon receipt of a drug shipment, the shipment must be logged into the IWRS. Study drug accountability records must also be maintained that include the subject number to whom the study drug was dispensed and the date, quantity and lot number of the study drug dispensed.

Depending upon the decision of Gilead Sciences, remaining unused study drug supply will be returned to Gilead Sciences or its designee after the study is completed or will be discarded or destroyed at the clinical site. If the study drug is discarded or destroyed at the clinical site, standard institutional policy should be followed and be readily available for review by Gilead Sciences and/or its designee. Records documenting the date of study drug shipping or destruction, relevant lot numbers, and amount shipped or destroyed should be maintained.

#### 5.2.2.7. Overdose Precautions

Ofatumumab doses as high as 2,000 mg have been administered without inducing excessive toxicity {[Coiffier 2008](#), [Coiffier 2010](#), [Wierda 2010](#)}. Accordingly, for this protocol, an overdose is defined as infusion of >2,000 mg of ofatumumab in a single day. In a subject who experiences an overdose, any further ofatumumab infusion on that day should be interrupted. Observation for any symptomatic side effects should be instituted, and biochemical and hematological parameters should be followed closely (consistent with the protocol or more frequently, as needed). Appropriate supportive management to mitigate adverse effects should be initiated, as necessary.

The Gilead Sciences medical monitor should be contacted if an ofatumumab overdose occurs. Cases of ofatumumab overdose may result in specific reporting requirements (see Section 8.6).

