Ofatumumab has recently received approval in Europe and in the United States for the treatment of patients with previously treated CLL {Gravanis 2010, Lemery 2010, Wierda 2010}. In the pivotal Phase 2 trial, all patients received 8 weekly infusions of ofatumumab followed by 4 monthly infusions during a 24-week period; the dose of the initial infusion was 300 mg and the dose of the remaining 11 infusions was 2,000 mg. The primary efficacy population comprised 59 patients with CLL refractory to fludarabine and alemtuzumab. Also accrued was a population of 79 patients who had fludarabine-refractory disease and bulky lymphadenopathy (ie,  $\geq 1$  nodal mass  $> 5$  cm in diameter). The overall response rates were 58% and 47% and the median PFS values were 5.7 months and 5.9 months for the 2 groups. Median neutrophil counts were stable during treatment and improvements in thrombocytopenia and anemia were observed. The most frequent adverse events were infusion reactions and infections. Infusion reactions were common during the first 2 doses, typically subsiding with subsequent drug administrations. The rates of infection were consistent with historical data {Perkins 2002, Tam 2007} when considering the extent of CLL, the amount of prior therapy, and the level of pre-existing immunosuppression among the study participants.

The 2000-mg dose selected for the Phase 2 study was based on data indicating that the mass of CLL tumor affected the clearance of the drug, with high elimination rates in patients with bulky lymphadenopathy {Coiffier 2008, Coiffier 2010}. The data suggested that the 2000-mg dose offered necessary target coverage in patients with high-volume CLL. In patients with lower tumor burden, drug concentrations were better maintained. The data supported use of lower ofatumumab doses in patients receiving concomitant therapy that could reduce tumor volume. Nonclinical data have indicated that exposure values consistent with a 1000-mg clinical dose are sufficient to provide saturation of the CD20 target {Bleeker 2008}. Based on these collective data, current trials for patients with previously treated CLL use a 1000-mg dose of ofatumumab when giving the drug as a component of combination therapy.

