### 5.3. Study Drug Administration

#### 5.3.1. Overview of Dosing Regimen

[Table 5-1](#) provides information regarding the planned dosing regimen. All subjects will receive the recommended premedication ~30 to ~60 minutes (or per institution-specific standard) before the ofatumumab infusion. In Arm A, idelalisib will be administered together with the premedication ~30 to ~60 minutes before the ofatumumab infusions. For both treatment arms

(Arm A and Arm B) the first infusion of ofatumumab will be administered at a dose of 300 mg. At each of Visits 3 through 13, subjects on both arms will be given the recommended premedications, and ofatumumab will be infused at a dose of 1,000 mg (Arm A) or 2,000 mg (Arm B).

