**Table 5-3. Study Drug (Ofatumumab) Infusion Rates**

Interval After Start of Infusion, min	Arm A		Arm B		
	Infusion 1 (300 mg), ml/hr	Infusion 2-12 (1,000 mg), ml/hr	Infusion 1 (300 mg), ml/hr	Infusion 2 (2,000 mg), ml/hr	Infusion 3-12 (2,000 mg), ml/hr
0-30	12	25	12	12	25
31-60	25	50	25	25	50
61-90	50	100	50	50	100
91-120	100	200	100	100	200
> 120	200	400	200	200	400

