### 5.3.3.3. Management of Infusion Toxicity

Ofatumumab can cause infusion reactions manifesting as bronchospasm, dyspnea, laryngeal edema, pulmonary edema, flushing, hypertension, hypotension, syncope, cardiac ischemia/infarction, back pain, rigors, abdominal pain, pyrexia, rash, urticaria, and angioedema {[Coiffier 2008](#), [Glaxo Group Limited 2011](#), [Wierda 2010](#)}. Reactions are typically more frequent and severe during the first infusion and are generally less frequent and less severe with subsequent infusions. In the Phase 2 pivotal trial {[Wierda 2010](#)}, infusion reactions occurred in 44% of patients on the day of the first infusion (300 mg), in 29% of patients on the day of the second infusion (2,000 mg), and less frequently during subsequent infusions. The time to onset of infusion toxicity may range from 30 to 120 minutes.

Subjects should be monitored (including vital signs approximately every 15 minutes) for infusion toxicity for ~1 hour following the administration of the first and second infusions, or until vital signs return to normal or baseline for subjects who experience infusion toxicity during any infusion. If a subject has not experienced infusion toxicity during the first 2 infusions, it is acceptable to perform a final vital signs check 15 to 30 minutes after the end of subsequent infusions.

Patients with pre-existing pulmonary or cardiac conditions, those who experienced prior cardiopulmonary adverse reactions to ofatumumab, and those with high numbers of circulating malignant cells ( $\geq 25 \times 10^9/L$ ) may be at particular risk. For example, in a study of patients with moderate to severe chronic obstructive pulmonary disease, 2 of 5 patients developed Grade 3 bronchospasm during infusion {[Glaxo Group Limited 2011](#)}.

If an infusion reaction Grade  $\leq 2$  occurs, the infusion may be temporarily slowed or interrupted and then can be restarted when the subject's condition has stabilized. Upon restarting, the infusion rate should be half of the infusion rate at the time the infusion was paused but not less than 12 mL/hour. After resuming the infusion, the infusion rate may be increased consistent with [Table 5-3](#) based on patient tolerance.

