- The ofatumumab dosing regimen (including the ofatumumab dose of 2000-mg/infusion) selected for the control arm (Arm B) of this study is the approved dose in product labeling {[Glaxo Group Limited 2011](#)}. Phase 1 pharmacodynamic data have suggested that this dose is appropriate to achieve CD20 target coverage when using ofatumumab as a single agent in patients with advanced, bulky lymphadenopathy {[Coiffier 2010](#)}.
- The ofatumumab dose of 1000 mg/infusion to be used in combination with idelalisib in the investigation arm (Arm A) of this study is supported by nonclinical and clinical data. Nonclinical data have indicated that exposure values consistent with a 1000-mg clinical dose are sufficient to provide saturation of the CD20 target {[Bleeker 2008](#)}. The findings of the Phase 1 pharmacodynamic study of ofatumumab suggest that this dose is appropriate in patients receiving concomitant therapy that could reduce tumor volume {[Coiffier 2010](#)}. Based on these collective results, current trials for patients with previously treated CLL use a 1000-mg dose of ofatumumab when giving the drug as a component of combination therapy. It is further conjectured that mobilization of CLL cells from sanctuary sites into the peripheral blood may enhance ofatumumab-mediated CLL cell killing. Additional benefits resulting from the lower ofatumumab dose may include reductions in the frequency and severity of ofatumumab-dependent infusion reactions and in the duration of ofatumumab administration.
- Administration of ofatumumab therapy for 24 weeks is consistent with recommendations in the ofatumumab package insert {[Glaxo Group Limited 2011](#)} and matches the total planned durations of drug administration typically employed with other antibodies (eg, alemtuzumab {[Keating 2002a](#)} or rituximab {[Robak 2010](#)}) used in the therapy of previously treated CLL.
- In a Phase 1/2, single-arm, dose-ranging study, concomitant administration of idelalisib at a dose of 150 mg BID together with ofatumumab at a dose of 1,000 mg has been shown to be safe and active {[Barrientos 2012](#), [Furman 2012](#)}.
- Consistent with the current product package insert for ofatumumab, subjects who are HBc antibody positive at screening will be monitored for HBV reactivation (manifest as detectable HBV DNA by quantitative PCR). Subjects will be tested monthly for the duration of ofatumumab therapy and every 3 months thereafter for 1 year from the end of therapy.

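### Ofatumumab overdose is set at more than 2,000 mg a day for everyone, which leaves up to 6.7 times the assigned dose at infusion 1, and up to 2 times in Arm A afterwards, outside the overdose instructions

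*Protocol*

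**What the plan says.** Section 5.2.2.7 notes that doses up to 2,000 mg have been given without undue toxicity, citing three reports, and concludes that "an overdose is defined as infusion of >2,000 mg of ofatumumab in a single day". It makes no distinction by arm or infusion number. When an overdose occurs, that day's infusion is to be interrupted, the subject observed, laboratory values followed closely and the sponsor's medical monitor contacted.

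Section 5.3.1 sets the assigned doses: 300 mg at infusion 1 in both arms, then 1,000 mg (Arm A) or 2,000 mg (Arm B) at infusions 2-12.

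For idelalisib, section 5.2.1.8 uses a different kind of rule. It records that no maximum tolerated dose was reached at 350 mg BID, yet says that "an overdose is defined as administration of more than the prescribed daily dose".

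On experience, section 1.1 says of the pivotal ofatumumab study that "the dose of the initial infusion was 300 mg and the dose of the remaining 11 infusions was 2,000 mg". Section 5.10 says that idelalisib "together with ofatumumab at a dose of 1,000 mg has been shown to be safe and active", and section 1.3.5.2.2 gives that combination schedule as 300 mg followed by 1,000 mg infusions.

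**The concern.** The threshold is inferred from tolerability of 2,000 mg but applied to infusions whose assigned dose is much lower. A subject in either arm who receives 2,000 mg at the first infusion, or an Arm A subject who receives the full Arm B dose later, has not had an overdose under section 5.2.2.7. The instruction to stop before any reaction appears therefore does not apply.

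Section 5.2.2.5 puts every dose in a 1,000-mL bag, and Table 5-3 sets the pump in mL/hr. An over-filled bag thus raises the mg/hr by the same factor as the dose. The later Arm A and Arm B doses differ only by one or two vials of the same 1,000-mg size. Stopping early is the step that limits exposure.

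**Working it through.** **Inputs.** Threshold: 2,000 mg (5.2.2.7). Assigned doses: 300, 1,000 and 2,000 mg (5.3.1). Bag volume: 1,000 mL (5.2.2.5). Pump rates: Table 5-3.

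**Threshold divided by assigned dose.**

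| Infusion | Assigned dose | Ratio |
|---|---|---|
| 1, both arms | 300 mg | 2,000/300 = 6.7 |
| 2-12, Arm A | 1,000 mg | 2,000/1,000 = 2.0 |
| 2-12, Arm B | 2,000 mg | 2,000/2,000 = 1.0 |

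Only the last row fits the definition.

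**A 2,000 mg bag at infusion 1, run without interruption.** The concentration is 2,000/1,000 = 2 mg/mL. The rates are 12, 25, 50 and 100 mL/hr for 30 minutes each, then 200 mL/hr.
- Volume in the first 2 h: 6 + 12.5 + 25 + 50 = 93.5 mL.
- The assigned 300 mg is 150 mL, reached at 2 + (150 - 93.5)/200 = 2.28 h.
- The bag ends at 2 + (1,000 - 93.5)/200 = 6.53 h.
- When the assigned dose is passed, 1,700 mg and about 4.25 h remain.
- Final-step rate: 200 x 2 = 400 mg/hr, against 200 x 0.3 = 60 mg/hr planned, again 6.7-fold.

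**A 2,000 mg bag in Arm A, infusions 2-12.** The rates are 25, 50, 100 and 200 mL/hr for 30 minutes each, then 400 mL/hr.
- Volume in the first 2 h: 12.5 + 25 + 50 + 100 = 187.5 mL.
- The assigned 1,000 mg is 500 mL, reached at 2 + (500 - 187.5)/400 = 2.78 h.
- The bag ends at 2 + (1,000 - 187.5)/400 = 4.03 h.
- When the assigned dose is passed, 1,000 mg and about 1.25 h remain.

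**Rates for 2,000 mg, Arm A against Arm B.** At infusion 2, Arm B's column "Infusion 2 (2,000 mg), ml/hr" runs from 12 to 200, which is 24 to 400 mg/hr at 2 mg/mL. Arm A's column runs from 25 to 400, which would give 50 to 800 mg/hr, or 2.0 to 2.1 times as fast. At infusions 3-12 the two columns are identical, so there is no rate difference.

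**Described experience against the cases outside the definition.** The pivotal study reached 2,000 mg only after a 300 mg first infusion, and the combination study used 1,000 mg. Neither includes 2,000 mg as a first infusion or with idelalisib. The other two reports cited in 5.2.2.7 are Phase 1-2 ofatumumab work whose first-infusion doses the protocol does not give. Nothing is claimed about them.

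**The case against.** The case for leaving the text alone has real content.

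- **It is a toxicity ceiling, not permission.** Section 5.3.1 fixes each dose and section 5.2.2.6 bars use other than as directed. A reader might infer that the protocol tolerates 6.7 times the first dose or lets it go unreported. It does neither: section 8.6 makes medication errors reportable within 24 hours.
- **Reaction rates.** Section 5.3.3.3 reports reactions in 44% of patients at the 300 mg first infusion, and a reader might take this as evidence that excess dose is the hazard. The same sentence gives 29% at the 2,000 mg second infusion. The pattern is one of first exposure, not of dose.
- **Arm A.** Section 5.10 gives 2,000 mg as the labelled dose and does not present 1,000 mg as a safety limit with idelalisib. From infusion 3 on, the worst case is the Arm B dose at Arm B's own rates.
- **Section 8.6.1.** A reader might infer a flat contradiction with the general overdose definition. That text refers to a maximum recommended dose but also to the individual subject's daily dose. It is ambiguous, so a contradiction is not shown.
- **Timing and likelihood.** Reaction onset is put at 30 to 120 minutes, before the 2.28 h at which an assigned-dose rule would trigger at infusion 1. Someone must also notice the wrong bag. The 300 mg dose uses different vials from the 2,000 mg dose.

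These points narrow the concern but do not remove it. The infusion-reaction rules act only after a reaction and allow a restart once it eases. Medication-error reporting is notification, not bedside management. At 2.28 h, 1,700 of the 2,000 mg has still not been given.

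**Conclusion.** The point holds as a limited patient-safety matter. Section 5.2.2.7 fits only Arm B infusions 2-12. Elsewhere it leaves up to 6.7-fold (infusion 1, both arms) and up to 2-fold (Arm A infusions 2-12) excesses outside its instructions. It is strongest at infusion 1 and at Arm A infusion 2, and weaker at Arm A infusions 3-12.

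The effect is confined to acute management and to what is classed as an overdose. Efficacy results, sample size and error rates are untouched.

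The infusion times assume a correctly diluted 2,000 mg bag run at Table 5-3 rates without interruption. The protocol gives no dosing-error rate, so no frequency is estimated. The stronger statement, that the cited tolerability evidence as a whole fails to support the threshold, is not established, because two of the three reports are not described.

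**What to change.** In section 5.2.2.7, define overdose as infusion in a single day of more than the ofatumumab dose assigned for that infusion: 300 mg at infusion 1, thereafter 1,000 mg in Arm A or 2,000 mg in Arm B. This follows the approach of section 5.2.1.8 and removes the uncertainty about how the section relates to 8.6.1.

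The cost is one sentence, plus a few more events classed as overdose and called to the medical monitor. Dosing, data collection and analysis do not change.

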#### 5.2.2.8. Exposure and Spill Precautions

Based on available data, ofatumumab does not appear to be irritative, acutely toxic, or genotoxic at levels that are likely to result from inadvertent exposure to the drug. No special precautions relating to exposure are required.

### 5.3. Study Drug Administration

#### 5.3.1. Overview of Dosing Regimen

[Table 5-1](#) provides information regarding the planned dosing regimen. All subjects will receive the recommended premedication ~30 to ~60 minutes (or per institution-specific standard) before the ofatumumab infusion. In Arm A, idelalisib will be administered together with the premedication ~30 to ~60 minutes before the ofatumumab infusions. For both treatment arms

(Arm A and Arm B) the first infusion of ofatumumab will be administered at a dose of 300 mg. At each of Visits 3 through 13, subjects on both arms will be given the recommended premedications, and ofatumumab will be infused at a dose of 1,000 mg (Arm A) or 2,000 mg (Arm B).

